A total of 8-10 community advisory board members (CAB), 42 student nurses from the UNMC Northern Division NRSG 413 Population Centered Care course, and 80 rural male subjects (40 per group) are needed to achieve the proposed objectives. The sample will consist of 80 men (40/group) who meet the inclusion criteria. Hertzog 74suggested that 30 participants per group in a pilot study is a sufficient sample size for aims involving between group differences and if the results are to be used to estimate the needed sample size for a future, fully- powered study. It is important for this study that we obtain reliable estimates of effect size with which to perform a power analysis for subsequent research, so 40 participants per group will be sought, for a total of 80. Some participants will likely not complete the study, so we will enroll 80 men to allow for up to a 30% attrition rate. Power for the repeated measures analysis of variance (RM-ANOVA) was determined using G*Power 3.1.9. A within-between interaction will be the primary test of significance (time*group interaction). Assuming a small effect size ($f=.10$),⁷⁵ a significance level of .05, 3 time points, and an estimate of .5 for the correlation between time points, 164 participants (82 per group) would be needed to have 80% power. Because this is a pilot study, a smaller sample size is justified, and the results of the pilot study will be used to update the power analysis prior to a future study.

Purposeful justification for the total number of community advisory board members and student nurses is based upon their information rich knowledge of the rural context as either community leaders or students in a rural college of nursing. Justification of the total sample size desired for the community advisory board is based upon optimal group function / interaction (8-10 persons) documented in previous advisory board work in agricultural based locales (Kingman, Yoder, Hodge, Ortega, & Field, 2004). Justification for inclusion of 42 student nurses was based upon the aim of the R-15 AREA NIH mechanism to expose undergraduate students to research. Community outreach is a concept taught in NRSG 413- Population Centered Care. It was deemed feasible to involve all students enrolled in this NRSG 413 course to the community outreach activity of this study- without excluding any student.

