UNMC Northern Division Student Nurses Enrolled in NRSG 413- Population Centered Care course receive training in community outreach / community engagement as an expected course outcome. Students in this course will spend 2 hours of their assigned course clinical time in group discussion with the principal investigator, [name], who is an advanced practice public health nurse. The discussion will involve planning community outreach and community engagement strategies for our study region that may enhance recruitment and retention of CAB members and subjects. Students will be asked to identify strategies for enhancing the planned community outreach and community engagement specific to rural populations for this study. Activities will include determining strategic recruitment material dissemination, creating community resource maps, and identifying community leaders and lay persons pivotal to enhancing community partnership. Prior to beginning the discussion, students will be asked to complete a short survey about their understanding of the public health nurse role in community outreach / community engagement. The students will be asked to complete the same survey post discussion to determine if the discussion experience enhanced their understanding of this role.

Intervention: The proposed feasibility study is a pragmatic RCT. Rural men (ages 40-69) will be recruited over a 12 month period to obtain a target enrollment of 80 subjects. Subjects will either be allocated to the intervention (Lose-It Premium with social comparison group, Wi-Fi scale for self-monitoring, plus SMS support messages for weight loss- MT+) (n=40) or the comparison group (Lose-It Basic- MT) (n=40). These group sizes reflect oversampling by 30% in each group to allow for attrition, based upon attrition rate averages.

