Following informed consent and completion of baseline visit, eligible participants will be randomized 1:1 to either intervention or comparison group. Participants randomized to the MT+ group will receive *Lose-It* Premium version (value \$40) and Wi-Fi Nokia Body+ scale (\$100). Participants randomized to the MT group will receive *Lose-It* Basic version (free) plus a \$25 stipend for their participation in each assessment point (3). The men will be randomly assigned to the intervention and comparison groups as they are enrolled using an allocation schedule created by the project statistician. The research nurses will not be blinded to the group assignment as they must conduct the app download on the subject's phone and conduct orientation training of the app with the subject that is specific to their assignment (basic app vs. premium app). Randomization will be predetermined using a random number generator and urn randomization to ensure equal sample sizes.

A comparison group (MT) (n=40) of men will receive the *Lose-It* Basic app. The basic app permits daily self-monitoring of eating and physical activity and manual logging of daily weight. MT participants will be asked at baseline to self-monitor their eating, activity, and weight daily. They will receive no text message prompts for self-monitoring, self-monitoring trend reports, or peer interaction via group. MT participants will complete assessments at baseline, 3 and 6 months postbaseline. MT participants will only receive text message reminders for their assessment visit appointment times.

Description of the Intervention Group (MT+). *Lose-It* Premium permits enhanced customization of goal setting, app automated self-monitoring reminders, customized email reports that outline self-monitoring trends important in supporting motivation and confidence during periods of behavioral action. The Nokia Wi-Fi scale will provide automated coaching, rewards and recording of weight synced to the *Lose-It* app permitting immediate feedback and visual maps of weight trends.

Research Staff Support-Reminder Prompts: MT+ participants will have research staff support available via phone. They will also receive reminder prompts for self-monitoring via text and phone when non-adherence with self-monitoring of dietary intake, physical activity or weight is incomplete for 5 days of greater.

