Lose-It Account Retention Option for Subjects at end of Study: As subjects have matriculated through our study, many have requested their desire to retain their Lose-It account food log and physical activity data. Because we set up the accounts using dummy username and passwords- the men are not able to retain their log information in Lose-It (basic or premium accounts) unless we conduct a username and password change of ownership. We consulted with our community advisory board members on 1-14-19- whom

were in full support of offering subjects an option to change ownership of their Lose-It account upon study completion. We have written and tested a procedure for changing username and password (See Protocol for Lose-It accounts at the end of the study document) that will permit the subjects to select/input a password that is not known to us which will ensure the privacy of their Lose-It account after the time of password change. We will inform the subjects of this option for change of ownership at their 6-month visit, at which time a revised written consent will be obtained. For those subjects who have already completed the six month visit, we will contact them by text and email informing them of the option. Those completers who desire this option will be provided a telephone call during which an electronic version of the revised written consent will be obtained (as consistent with our procedures for obtaining informed consent at point of enrollment).

Focus Groups. Two evaluative focus groups will be held at 6 months post-baseline with a purposive sample of intervention group completers stratified according to their weight loss outcome (successful/unsuccessful in achieving 5% baseline body weight loss) to solicit their perceptions on the MT+ intervention efficacy, including acceptability/feasibility.¹⁰⁷ Use of two focus groups permits cross-case comparative analysis of the intervention.^{70, 108} Focus group participants will receive \$25 for their attendance and will be asked to maintain confidentiality of the contents of the focus group discussion. The 90-minute focus groups will be held at the same community center as the assessments and audio recorded. The PI, an experienced focus group moderator, will lead the discussion with a semi-structured interview guide informed by the tenets of the social ecological perspective and study aims. The focus group

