Aim #2: Determine preliminary efficacy of a MT+ intervention to a comparison group receiving only a basic self-monitoring app (MT) in achieving 1) weight loss (primary), and 2) improved diet and increased PA (secondary) at 3 months post-baseline and follow-up at 6 months post-baseline in rural men. The efficacy analyses for aim 2 will be tested via RM-ANOVA models, as they provide a direct measure of differences between the intervention and comparison groups in weight loss and dietary and PA behaviors across the study, as well as effect size estimates. Huynh-Feldt corrected F-tests will be used in order to account for any possible violation of sphericity. If there is a higher than expected attrition rate, a maximum likelihood estimation method (e.g. mixed models) will be used instead of RM-ANOVA in order to utilize all available data and not delete cases in a listwise manner. Overall weight lost at follow-up will be assessed via an independent groups t-test. Outcome variables that are not normally distributed will either be transformed or assessed with nonparametric methods.

Aim #3: Determine quantitative and qualitative indicators of community capacity (resource mobilization, learning opportunities-skills development, partnership linkages, participatory decision- making, leadership) to support a relevant weight loss intervention for rural men. For aim 3, multiple indicators of community capacity will be used to evaluate support for the weight loss intervention applying best practice recommendations (113), 1) CAB- assessed community capacity change survey report by CAB, participation level of members (i.e. # meetings, activities, resources allocated, partnership/network linkages, leadership roles assumed), member attrition with reasons, Qualitative indicators of community capacity in CAB include perceived benefits/skills gained, barriers and facilitators of retention, proposed strategies to increase retention, CAB evaluation of student outreach activities, 2) STUDENTS- clinical log of community outreach activities (type, number, hours) developed, implemented, and outcome,

leadership activities (dissemination via honors projects, clinical conference and class presentations). Qualitative indicators of community capacity among students will include perceived skill development, and leadership confidence. Graduate level students help in training sessions, data collection and implementation of intervention.

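### At the stated 30% attrition allowance, 40 per group leaves 28, below the pilot benchmark of 30 that the plan cites; 40 keeps 30 only up to 25% attrition

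*Combined protocol and SAP*

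**What the plan says.** The Accrual section argues in steps. It cites pilot-study guidance that "30 participants per group in a pilot study is a sufficient sample size for aims involving between group differences". It then says that effect-size estimates from this trial will feed a later power calculation, "so 40 participants per group will be sought, for a total of 80". The next sentence reads: "Some participants will likely not complete the study, so we will enroll 80 men to allow for up to a 30% attrition rate". The same section calculates that 164 men would give 80% power for a small effect, and sets that number aside because this is a pilot.

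The Methods section, under Intervention, describes the same 40 per group differently: "These group sizes reflect oversampling by 30% in each group to allow for attrition, based upon attrition rate averages". Allocation is equal: "eligible participants will be randomized 1:1 to either intervention or comparison group".

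Under Aim #2 in Statistical Analysis, RM-ANOVA is the default efficacy analysis. The exception is: "If there is a higher than expected attrition rate, a maximum likelihood estimation method (e.g. mixed models) will be used instead of RM-ANOVA". Its stated purpose is "in order to utilize all available data and not delete cases in a listwise manner".

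No section gives a number of completers to be protected, the base to which the oversampling was applied, or the attrition rate that counts as expected.

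**The concern.** An attrition allowance means something only in relation to the number that should be left afterwards. The plan names two sample-size standards, 30 per group and 164 in total, and adopts only the first. A reader will naturally take 40 as 30 plus a cushion, and will take the cushion to be good for a 30% loss. It is not.

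Completers are the relevant count because, by the plan's own account, the default RM-ANOVA drops men with incomplete data. The trial's main quantitative product is an effect-size estimate for planning a larger study. Whoever uses it should know how many men per group may stand behind it at the attrition the plan says it can absorb, and whether the cited benchmark is then met.

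**Working it through.** **Inputs.** Enrolled: 40 per group, 80 in total, 1:1 (Accrual; Methods). Benchmark: 30 per group (Accrual). Attrition allowance: up to 30% (Accrual). Oversampling: 30% in each group, base not stated (Methods, Intervention). Power assumptions: f = .10, alpha .05, 3 time points, correlation .5 (Accrual). Attrition is taken as equal in both groups.

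**The plan's own power figure.** For the time-by-group interaction, noncentrality = f² × N × m / (1 − ρ), with df1 = 2 and df2 = 2(N − 2). At N = 164 the noncentrality is 0.01 × 164 × 3 / 0.5 = 9.84 and the power is 0.805. At N = 162 the power is 0.7998. The smallest even N is therefore 164, as stated.

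**Men left at the stated allowance.** 40 × (1 − 0.30) = 28 per group, 56 in total. Shortfall against the benchmark: 30 − 28 = 2 per group.

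**Attrition at which 30 per group is kept.** 1 − 30/40 = 25%, or 20 of 80 men lost.

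**The oversampling sentence, two readings.**
- Literal: 40 is 1.3 times a base. The base is 40/1.3 = 30.8, and the attrition absorbed is 1 − 1/1.3 = 23.1%.
- Loose: 30% of those enrolled may be lost. Methods then agrees with Accrual, but the number protected is 28, still below 30.

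**What two men per group are worth.** The 95% half-width for a difference between two means, in SD units, is t(.975, 2n − 2) × √(2/n).

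| Per group | Half-width (SD) | Total N | Interaction power at f = .10 |
|---|---|---|---|
| 28 | 0.536 | 56 | 0.347 |
| 30 | 0.517 | 60 | 0.370 |

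The half-width rises by about 0.02 SD and the power falls by about 0.02, in a trial that the plan already says is not fully powered.

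**The case against.** The strongest reply is that nothing stated is broken. The cited guidance speaks of participants, not completers, and 40 enrolled exceeds 30. The plan also gives a separate reason for 40, namely good effect-size estimates, before it mentions attrition. It may simply tolerate 28 completers. This stands in part: the plan sets no minimum number of completers, and treating 30 as the number to protect is an inference from the order of the argument. But if 28 is tolerated, the plan does not say so. If 40 is itself the number wanted at the end, enrolling 40 leaves no allowance at all, since 40/0.70 = 57.1, or 58 per group.

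A reader might also infer that Accrual and Methods contradict each other, 30% against 23.1%. The documents do not establish that. The 23.1% needs a base of 30.8 men, which appears nowhere, and the oversampling sentence may be loose wording for the same 30%. Nor is 23.1% the point at which the trial falls below 30; that point is 25%.

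A third possible reply is that the mixed-model fallback removes the problem. It applies only above an expected attrition rate that the plan does not define, so it cannot be relied on at 30%. For the same reason, the opposite inference is not supported either: that losses of 21 to 24 men (26.25% to 30%) would leave RM-ANOVA running on 56 to 59 completers. That holds only if the expected rate is 30%, and Accrual gives 30% as a ceiling, not an expectation.

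**Conclusion.** The point holds as a mismatch in the sample-size justification. At the attrition the plan says it allows for, 28 per group remain against a cited 30; the benchmark is kept only up to 25%. This assumes equal attrition in the two groups and that the benchmark is meant to apply to men who complete. With uneven losses one group would be smaller still: 56 completers could be 30 and 26.

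It would be tempting to conclude that the trial is under-enrolled and should have taken 30/0.70 = 42.9, so 43 per group. The documents do not support that, because they call 30 sufficient and never make it a required number of completers.

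Severity is minor: the loss of precision is about 0.02 SD in half-width. Confidence is high for the arithmetic and moderate for 30 being the number to protect.

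**What to change.** **Accrual.** Replace the attrition sentence with: *Eighty men (40 per group) will be enrolled. The cited benchmark of 30 per group is retained for attrition up to 25%; at 30% attrition about 28 per group would remain.*

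**Methods, Intervention.** Replace the oversampling sentence with: *Forty per group is the enrolled number; the attrition allowance is as stated under Accrual.*

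Neither edit should call 30% the expected rate. Statistical Analysis leaves that term undefined, and defining it here would fix the switch from RM-ANOVA to mixed models as a side effect. Leave the Aim #2 analysis text as it is.

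**Cost.** Two sentences. Enrolment, analysis and the switch to mixed models are unchanged. The plan would state a slightly less favourable allowance and admit a gap of 2 per group at 30%. The Methods sentence being replaced also carries the only stated basis for the rate (average attrition); if that is to be kept, it can move to Accrual. The section on retaining Lose-It accounts refers to men who had finished follow-up ("For those subjects who have already completed the six month visit"), so this corrects the record and does not redesign the trial.

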
Purpose

The specific aims of this study are:

Aim #1: Determine the feasibility and acceptability of a MT+ intervention for achieving weight loss in rural overweight and obese men. The aim will specifically address groups by 1) participation rates including number of men recruited and randomized over a 6 month period; 2) retention rates; 3) feasibility, usability, satisfaction ratings; 4) adherence record of logging by men in the intervention group; and 5) evaluative focus group feedback.

Aim #2: Determine preliminary efficacy of a MT+ intervention to a comparison group receiving only a basic self-monitoring app (MT) in achieving 1) weight loss (primary), and 2) improved dietary and PA behaviors (secondary) at 3 months post-baseline and follow-up at 6 months post-baseline in rural men.

Aim #3: Determine quantitative and qualitative indicators of community capacity (resource mobilization, learning opportunities-skills development, partnership linkages, participatory decision-making, and leadership) to support a relevant weight loss intervention for rural men.

Feasibility Substudy Aim: To determine the feasibility of men currently enrolled in our clinical trial to wear an activity sensor (Actigraph GT9X) for seven continuous days to objectively measure their continuous physical activity among the total volume of activity bouts across three gait dimensions: intensity, symmetry, and variability.

Background and Rationale

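### Only MT men are stated to be paid for assessment visits, so payment is confounded with arm for retention, and unequal dropout of unknown direction could bias the completer comparison of weight.

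*Combined protocol and SAP*

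**What the plan says.** The Methods section (Intervention paragraphs) sets out what each arm gets. "Participants randomized to the MT+ group will receive" the paid version of the app, valued at $40, and a Wi-Fi scale valued at $100. MT men get the free app and a $25 "stipend for their participation in each assessment point (3"). No visit payment is stated for MT+ men there or elsewhere.

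The same section fixes the order of events: "Following informed consent and completion of baseline visit, eligible participants will be randomized 1:1".

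Two other payments to the men appear. The Focus Groups paragraph gives $25 to MT+ completers "for their attendance and will be asked to maintain confidentiality of the contents of the focus group discussion"; there are two groups of eight. The accelerometer sub-study gives $25 for returning the device, and either arm may join.

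The Purpose section lists among the Aim 1 outcomes, to be addressed by group, "2) retention rates; 3) feasibility, usability, satisfaction ratings". Statistical Analysis, Aim #2, tests weight by RM-ANOVA and adds: "Overall weight lost at follow-up will be assessed via an independent groups t-test". A mixed model replaces the RM-ANOVA only if attrition exceeds expectation, and the plan says the purpose of the switch is to avoid listwise deletion. Accrual and Methods both allow for 30% attrition. The plan does not discuss the payment difference.

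**The concern.** The two arms have different reasons to come back. An MT man who skips a follow-up visit forgoes $25. An MT+ man already has his goods and, unless chosen for a focus group, loses nothing. The total value handed out may have been meant as rough balance, but goods given at baseline do not reward later attendance.

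Two things are at stake. First, retention by arm is meant to inform whether MT+ is feasible and acceptable. With payment fully aligned with arm, neither a difference nor the absence of one can be read that way, and no analysis can separate the two. Second, the RM-ANOVA as planned and the follow-up t-test use only men with follow-up weights. If men who lose less weight are more likely to leave, the arm that loses more men looks better than it is. Accrual says the pilot's effect-size estimates will feed the power analysis of a later trial, so such a distortion would carry forward.

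**Working it through.** **Payments (Methods).**

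| | MT | MT+ |
|---|---|---|
| Cash at baseline visit | $25 | none stated |
| Cash at month 3 | $25 | none stated |
| Cash at month 6 | $25 | none stated |
| Goods at baseline | $0 | $40 + $100 = $140 |
| Total | $75 | $140 |

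The gap in total value is $140 − $75 = $65 in favour of MT+. Randomization comes after the baseline visit, so the baseline $25 cannot affect retention after randomization. What remains is 2 × $25 = $50 in MT against $0 in MT+. The focus-group payment reaches at most 2 × 8 = 16 of 40 MT+ men.

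**Attrition allowance.** The plan states: "The sample will consist of 80 men (40/group) who meet the inclusion criteria". At 30% attrition, 40 × 0.70 = 28 men per arm complete. The plan gives no rates by arm.

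**Bias in a completer contrast.** The plan gives no figure for this, so the inputs are assumptions: no true effect; SD of 6-month change 5.5% of body weight; correlation r between weight loss and staying in of 0.3 to 0.5; dropout 15% in one arm and 30% in the other. With a normal latent tendency to stay and retained proportion p, the mean standardised weight loss among those retained is r × φ(c)/p, where c = Φ⁻¹(1 − p).

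- p = 0.70: φ(c)/p = 0.348/0.70 = 0.497
- p = 0.85: φ(c)/p = 0.233/0.85 = 0.274
- Difference: 0.222
- Bias at r = 0.3: 5.5 × 0.3 × 0.222 = 0.37 points
- Bias at r = 0.5: 5.5 × 0.5 × 0.222 = 0.61 points

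The sign favours the arm with 30% dropout, whichever arm that is. With 10% against 30% dropout (p = 0.90 gives 0.195; difference 0.302) the range is 0.50 to 0.83 points. With r = 0, or with equal dropout, the bias is zero.

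**Scale of that bias.** At 15% against 30%, completers number 34 and 28, and the standard error of the contrast is 5.5 × √(1/34 + 1/28) = 1.40 points. The bias is 0.37/1.40 = 0.26 to 0.61/1.40 = 0.44 of a standard error.

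**Would the fallback respond?** Overall attrition is (15 + 30)/2 = 22.5%, or (10 + 30)/2 = 20% in the wider case. If the expected rate is read as the 30% allowance, neither exceeds it, so the listwise RM-ANOVA stands. The t-test has no stated missing-data provision in any case.

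**Precision of the retention comparison.** With 40 per arm, power at two-sided 5% is about 18% for 70% against 80% retention and 61% for 70% against 90%. A true imbalance could easily go unremarked.

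**The case against.** Paying cash to the arm that receives no goods is a defensible choice, and MT+ men come out ahead in total value. MT+ men also get phone support, prompts when self-monitoring lapses, an early follow-up call and a moderated peer group. The stipend may therefore offset higher dropout in MT rather than create an imbalance. Even with equal payment, the extra staff contact would still complicate a retention comparison. Aim 1 is described as largely descriptive, with no test of retention between arms. Nothing in the documents links $50 to a dropout gap of 15 or 20 points, and the illustrated bias is under half a standard error at 15% against 30%. The consent form is not in the text available, so MT+ non-payment rests on the Methods wording, which does read as a contrast between arms.

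Much of this stands. A reader might infer that the design tilts the weight result toward MT+. The documents do not support that: the net direction of dropout is unknown, and the bias reverses if MT loses more men. A reader might also infer that MT+ men are uncompensated or have no payment that depends on completing; the goods and the focus-group payment contradict both. What the objection does not remove is that payment tied to attendance differs by arm, that retention is an outcome, and that the fallback looks at overall attrition and not attrition by arm.

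**Conclusion.** The point holds as a matter of design. As written, $50 against $0 depends on attending the two visits after randomization, apart from the focus-group payment, so retention by arm is confounded with payment. This part needs no assumption beyond the Methods section stating all visit payments.

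The effect on weight is conditional. It needs unequal dropout that is also related to weight loss; unequal payment alone does not establish either. Under the assumed inputs it is about 0.4 to 0.6 points at 15% against 30% dropout, in favour of whichever arm loses more men. That is modest beside the trial's own imprecision, but the planned switch to a mixed model would not be triggered. The matter is worth correcting because it is cheap and touches outcomes under two aims; it does not invalidate the trial.

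**What to change.** Pay the same amount for the month 3 and month 6 visits in both arms. The planned outlay is 40 × 3 × $25 = $3,000.

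- **$25 per follow-up visit to all 80 men:** 80 × 2 × $25 = $4,000, which is $1,000 more. MT pay falls from $75 to $50, and the gap in total value widens from $65 to ($140 + $50) − $50 = $140.
- **The same, keeping the MT baseline $25:** $4,000 + 40 × $25 = $5,000, which is $2,000 more. No one's pay is cut, and the gap becomes $190 − $75 = $115.

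Either needs a change to the consent wording. The wider gap in total value is the price of equal incentives to return.

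If MT+ men are in fact paid for visits, correct the Methods section to say so.

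Equal payment does not remove the difference in staff contact. Report retention by arm with reasons for leaving, and use the likelihood-based model for weight whatever the overall attrition. That model relies on data being missing at random, so add a sensitivity analysis that relaxes this. If payments can no longer be changed, state the difference as a limitation wherever retention is compared.
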